Phone: Study staff will offer to administer the survey to patients over the phone with patients. This may occur either immediately after the phone consent process or at a later mutually agreed upon time.

Paper: Patients who prefer to complete the survey on paper will be mailed a survey in their enrollment packet. Approximately 7 days after we send the enrollment packet, we will call these patients to remind them to complete the survey. Those who do not complete the First Survey will not fulfill the requirements for the study enrollment process and will no longer be further considered for the study.

For patients that are enrolled in our study, we will allow them to meet us at the VAMC to return the paper survey or any other study-related documents if it is more convenient for them. If an enrolled patient is unable to receive the survey packet or any other study materials by mail or MyHealthVet, then we issue these materials in-person at the VAMC. Please note that this also includes gift cards.

First Survey Incentive: We will require patients to return the First Survey in order to receive the \$10 incentive. Following the completion of the First Survey, study staff will send a First Survey incentive packet which will include a \$10 gift card and a letter that will thank the patient for completing the survey.

To track surveys completed online, we will frequently download completed surveys from the Qualtrics server and import these responses into our secure study database which will be housed behind the VA firewall. Our study database will notify us of patients who complete the survey online in Qualtrics, but have not yet been sent a gift card.

Randomization to screening for T2DM: Approximately 2 weeks before their Primary Care appointment, we will randomize participants into one of the two study groups: 1) Blood Test Group and 2) Brochure Group. 252 study participants will be randomly assigned to undergo screening for T2DM using an HbA1c test at the laboratory of their respective VA primary care clinic. Participants will have a 4/5 (80%) chance of being selected for the Blood Test Group and 1/5 (20%) chance of being selected for the Brochure Group. Our database will use a programmed algorithm that will give all participants the same chances of being randomized into these two groups.

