Following randomization, study staff will contact patients by phone and mail to notify them of the arm to which they were randomized. For those that are randomized to the Blood Test Group, we will obtain a preferred date for patients to complete the HbA1c blood draw and study staff will accordingly enter this order date in CPRS.

Baseline Data Collection – HbA1c lab order and talking points

Blood Test Group: Following the randomization process, for patients randomized to the Blood Test Group, study staff will enter an HbA1c blood test order into CPRS. Study staff will aim to set up the blood draw order on the same day as the patient's upcoming Primary Care appointment for convenience.

Information about HbA1c results: Once we obtain the HbA1c results, we will store the results in our study database and deliver to the patient and their primary care provider information about these results. We will then use the following categories based on American Diabetes Association and National Diabetes Prevention Program guidelines to interpret HbA1c results:

- Normoglycemia: If results are < 5.6 then participants will be given the "normoglycemia information"
- Prediabetes: If results are $5.7 - 6.4$ then participants will be given the "prediabetes information"
- Diabetes: If results are > 6.5 then participants will be given the "diabetes information"

HbA1c results and information will be immediately communicated to primary care providers via CPRS to give providers the opportunity to communicate HbA1c test results to their patients before the study team shares these results with the patients. Trained study staff will deliver the applicable information by phone approximately 1 week after the test results are available.

To guarantee that all participants receive some form of information related to their HbA1c results, we

will mail a brief one page sheet summarizing the applicable information with the letter for their Second Survey; patients should receive this around the time of the aforementioned phone call.

We will send this information via MyHealthVet Secure Messaging if we are unable to find a current address or if patients prefer this mode of communication. Given that this information is the heart of our research study, it is imperative that patients receive this information. Thus, we need as many modes of providing this information to patients as possible.

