Final Survey: We will issue a Final Survey packet approximately 11 months after participants complete the First Survey. This packet will include a letter with instructions for completing the survey in the same mode they used to complete the preceding surveys. This survey will take approximately 20 minutes to complete.

We will send these documents via MyHealthVet Secure Messaging if we are unable to find a current address or if patients indicate a preference to receive information through this channel.

For their convenience, patients will also be given the option to use MyHealthVet Secure Messaging to send any documents that need to be returned to study staff.

Upon completion of the Final Survey, we will mail an incentive packet, which will include a thank you letter and \$10 gift card.

12-month Weights: Patients routinely have their weights measured at each Primary Care visit. Thus participants will have weight measurements at the time of their scheduled Primary Care appointment or around the time of their recall appointment date. We anticipate that through usual care many participants will have another weight measurement 12 months (± 1 month) later.

Prior to the first Final Survey follow-up call, study staff will identify those who do not have a 12 month (± 1 month) weight measurement in CPRS and encourage these participants to go to their Primary Care clinic for a weight measurement.

Interviews among Participants with Prediabetes about Their Perceptions of a Prediabetes

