Diagnosis: To gain deeper understanding of patient perceptions of a prediabetes diagnosis and brief counseling, we will conduct approximately 30 semi-structured telephone interviews among a maximum variation purposive sample of patients who are newly diagnosed with prediabetes and have different levels of health literacy. We will focus on health literacy because of its strong relationship to patients' self-care behaviors, receipt of recommended preventive services, understanding of health information, and health outcomes. We will conduct the interviews by phone to minimize participant burdens and maximize the response rate. These participants will be invited to participate in the interview after the completion of the 3rd Survey, which we anticipate for most participants will be approximately 6 months after their HbA1c test. Interviews will consist of open-ended questions to elicit information on feelings about receiving a prediabetes diagnosis, understanding of prediabetes and behavioral recommendations, facilitators of and barriers to behavior change, uncertainties about prediabetes. We anticipate each interview will take 30 minutes. Interviews will be audio recorded and transcribed. Consent to audio record interviews will be obtained during the initial informed consent process, though participants may choose to participate without agreeing to be recorded. We will conduct data analysis concurrently with data collection and will stop conducting interviews once we have reached thematic saturation. *Prior to any contact with participants we will submit the interview guide for IRB approval. (Note: This has been approved by the IRB)*

Data Analysis

Weights: Patients of the VAAHS primary care clinics routinely have their weights measured at each primary care visit. Thus all participants will have a weight measurement in CPRS when they undergo brief counseling or review of health promotion literature. We anticipate that through usual care many participants will have another weight measurement 12 months (± 1 month) later. Participants who do not have a weight measurement in CPRS 12 months (± 1 month) later will be asked to come to the VAAHS primary care clinic for a weight measurement.

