8/10/2018 Update: We would like the ability to extract weight data, our primary outcome, for enrolled participants who have collected weights from other VA medical centers. We have identified a number of enrolled patients that either receive care at other VA medical centers during the winter or have moved out of state during the course of the study. Unfortunately, if either of these occur during the follow-up period, we are unable to collect weight data. While we have been able to still send and receive survey data from these participants, because our current medical record data (i.e., weight) data access is limited to the Ann Arbor VA Healthcare System, we are unable to collect weights that may have been collected at other facilities. By having the ability to expand our data queries to any VA facility from which our

participants may have received a weight, we will be able to achieve a greater percentage of study participants with baseline and FU data.

We will extract these data from VA CDW data queries.

12/19/2018 Update: We would also like to expand our previous amendment to also allow us to extract data for our secondary outcome analysis, which will include MOVE visits, metformin use, and HbA1c labs.

2/25/2019 Update: We would like to update the date range (March 2015 – December 2017) that was originally provided in our VA Research Data Privacy and Security Assessment form to coincide with our first and last randomization dates. Our first randomization occurred on 1/27/2016 and our final randomization occurred on 3/31/2017. Thus, we would like to update our data date range from 1/27/2015 – 7/1/2018. We strongly feel data one year prior to randomization and 15 months post randomization is sufficient for collecting data for all four timepoints and is consistent with what other similar projects (e.g., the VA DPP projects) have done. (Added 3/20/2019) Given that pre/post medical data (primarily lab and weight data, but also MOVE participation and metformin use) are not always assessed consistently for veterans, we are requesting to change the range of baseline and follow-up observation dates so that we can increase the probability of obtaining these data."

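### Baseline weight for the primary outcome is not defined: weights from before randomization, after arm notification, or after the HbA1c result or brochure can all serve, with no selection rule

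*Combined protocol and SAP*

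**What the plan says.** **Allocation comes first.** Under Randomization to screening for T2DM: "Approximately 2 weeks before their Primary Care appointment, we will randomize participants into one of the two study groups". The arm is then disclosed: "Following randomization, study staff will contact patients by phone and mail to notify them of the arm to which they were randomized".

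**The first weight follows.** Under 12-month Weights: "Thus participants will have weight measurements at the time of their scheduled Primary Care appointment or around the time of their recall appointment date". The next weight is expected 12 months (± 1 month) later.

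**A second description ties that weight to the intervention.** Under Data Analysis, Weights: "Thus all participants will have a weight measurement in CPRS when they undergo brief counseling or review of health promotion literature". The Analyses paragraph likewise counts the 12 months of the primary outcome from counseling in one arm and from literature review in the other.

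**Blood draw, counseling and brochure are loosely timed.** Staff aim for a draw on the appointment day, but also say "we will obtain a preferred date for patients to complete the HbA1c blood draw". Staff give the result by phone about 1 week after it is available, and the provider, who is informed at once, may give it sooner. The brochure is mailed with no date fixed relative to any weight; participants are asked to read it before the Second Survey.

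**The latest text widens the dates.** The 2/25/2019 update asks for data from one year before to 15 months after randomization. Its 3/20/2019 addition, noting that weights and other data are not consistently assessed, asks to "change the range of baseline and follow-up observation dates". It gives no baseline window per participant and no rule for choosing among several weights.

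**Analysis.** A two-sample t test compares weight change between arms, with multiple imputation for missing weights. No baseline adjustment and no imputation model are described.

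**The concern.** A baseline should be fixed by a rule that allocation cannot influence. Here the visit that the plan describes comes after participants know their arm, and the wider date range leaves the choice of weight to whoever builds the dataset. An analyst who picks the weight nearest to counseling or literature review would be using an anchor that differs between arms, and in some participants a weight taken after the intervention.

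Because the primary test is on unadjusted change, any mean difference between arms that is already in the baseline passes one-for-one into the contrast. Adjusting for a baseline that allocation has affected, or imputing from it, does not restore the lost comparison. A weight taken before randomization does not have this problem.

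**Working it through.** **1. Figures that can be reproduced.** Split: 315 × 4/5 = 252 and 315 × 1/5 = 63, as stated. Data range: the first randomization, 1/27/2016, less one year is 1/27/2015; the last, 3/31/2017, to 7/1/2018 is 15.0 months. Both ends match the update. Every participant therefore has at least 12 months before randomization inside the requested range. The documents give no alpha, power, effect size or SD for the primary outcome, so the sample size cannot be re-derived.

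**2. Timeline, in weeks from randomization.**

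| Event | Planned time |
|---|---|
| Arm notification | after 0, before the visit |
| Appointment and its weight | about 2 |
| Blood draw | aim: about 2; otherwise the preferred date |
| Staff counseling call | draw + time to result + about 1 |
| Brochure mailing | not fixed |

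With a draw at the visit, counseling falls at about week 3 or later, so the visit weight precedes it. For a draw at week *t*, and taking time to result as zero, staff counseling precedes a week-2 weight only if *t* + 1 < 2, that is *t* < 1. If the provider gives the result as soon as it arrives, *t* < 2 is enough. The preferred-date wording allows either. A weight taken around a recall date has no fixed place in this order.

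**3. What may serve as baseline.**

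| Source | Position of the weight |
|---|---|
| 12-month Weights | after randomization and notification |
| Data Analysis, Weights; Analyses | at counseling or literature review, so arm-specific |
| 2/25/2019 update with 3/20/2019 addition | baseline range changed; data from up to one year before randomization available |

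No text ranks these.

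**4. Illustration of size (assumed inputs).** Assume two-sided alpha 0.05, a common SD of weight change of 4 to 8 kg, and complete data.

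- SE = SD × √(1/252 + 1/63) = 0.141 × SD.
- Difference detectable with 80% power = (1.960 + 0.842) × SE = 0.395 × SD.
- If an amount *b* of that difference is already in the baseline, power = Φ((difference − *b*)/SE − 1.960).

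| SD (kg) | SE (kg) | Detectable difference (kg) | Power, *b* = 0.25 kg | Power, *b* = 0.5 kg |
|---|---|---|---|---|
| 4 | 0.56 | 1.58 | 65.5% | 48.2% |
| 6 | 0.85 | 2.37 | 70.7% | 59.9% |
| 8 | 1.13 | 3.16 | 73.2% | 65.5% |

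Example, SD 6 and *b* = 0.25: (2.368 − 0.25)/0.845 − 1.960 = 0.546, and Φ(0.546) = 70.7%.

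**5. How plausible is *b*?** It is a mean over the whole arm. The Summary projects 63 of the 252 tested participants in the prediabetes range. If early change were confined to them, *b* = 0.25 kg needs 0.25 × 252/63 = 1.0 kg each by the time of the baseline weight, which in the default sequence is before they know their result.

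**The case against.** The strongest reply is that the planned order already protects the comparison. The visit is about 2 weeks after randomization, the draw is aimed at that day, and the phone call comes about a week after the result. In those 2 weeks participants know only their arm, not an HbA1c value, and the Brochure Group receives only general health information. Early loss in the Blood Test Group that persisted would shrink the contrast rather than create one. This stands, and it is why the bias is judged small.

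Three stronger readings are tempting but unsupported:

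- A reader might infer that the baseline is always taken after randomization. The 2/25/2019 update makes earlier weights available, so the defect is the missing rule.
- A reader might infer that a substantial share of the effect is lost. With linear build-up, a baseline 1 month after counseling would remove 1/12 = 8% and one at 3 months 3/12 = 25%, but the documents neither plan nor report such delays.
- A reader might infer that attendance, and so missing baseline weight, differs by arm because only one arm has a lab order. Both arms were sampled for an upcoming appointment, and nothing shows that the order changes attendance. It is a possibility only.

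A fair objection to the remedy is that a weight up to 12 months older lengthens the change interval to roughly 12 to 24 months and adds drift and noise. That stands too: an earlier baseline should not be combined with an unadjusted test of change. Nor do the documents show how recent the recorded BMI was at eligibility, so some participants may have no weight in the window.

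**Conclusion.** The point holds as a gap in the definition of the primary outcome. The visit plan puts the first weight after unblinded allocation, the analysis text anchors it on an event that differs by arm, and the 2019 update widens the dates without saying which weight counts.

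In the default sequence the resulting bias is probably small and, if early change persists, toward the null. That is a judgment from the timeline; the documents do not allow its size to be computed. The power figures rest on an assumed SD of 4 to 8 kg, an assumed baseline shift and complete data, and show only how a modest shift would matter. The change should be made because it is cheap and removes a choice that could depend on allocation, not because serious bias has been shown.

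**What to change.** State one rule for both arms:

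1. **Anchor** baseline on the randomization date. Use the last VA weight on or before it, within the 12 months already requested.
2. **Fallback.** If there is none, use the first visit weight only if it precedes the HbA1c result (Blood Test Group) or the brochure mailing (Brochure Group). Otherwise treat baseline as missing and impute it. A fallback weight still follows notification, so report the number used by arm.
3. **Analysis.** Replace the unadjusted t test on change with a comparison of 12-month weight adjusted for baseline weight.
4. **Imputation.** Include the visit weight in the imputation model.
5. **Sensitivity.** Repeat the analysis with the visit weight as baseline.

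The cost is analysis-plan wording and a query of data already requested; the fallback also needs result and mailing dates from study records. Randomization ended on 3/31/2017, so visits cannot be changed, but the definition can. The downside is that some baseline weights will be months old and noisier, which adjustment limits but does not remove, and a few participants may need the fallback.

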Randomization to Brochure Group: The 63 participants randomized to the Brochure Group will not receive study ordered HbA1c blood tests. We will mail to Brochure Group participants general health promotion information developed by the VA National Center for Health Promotion and Disease Prevention. We will ask these patients to review this information prior to completing the Second Survey.

Second Survey: Participants in both study groups will be issued a Second Survey packet immediately after their HbA1c test results are available (Blood Test Group) or at the time of their primary care appointment and/or appointment recall date (Brochure Group). This packet will include a letter with instructions for completing the survey using the same mode as the First Survey, a paper version of the survey (if applicable) and (if applicable) a paper version of the aforementioned information about HbA1c results. We anticipate this survey will take approximately 20 minutes to complete.

We will send these documents via MyHealthVet Secure Messaging if we are unable to find a current address or if patients indicate a preference to receive information through this channel. For their convenience, patients will also be given the option to use MyHealthVet Secure Messaging to send any documents that need to be returned to study staff.

Upon completion of the Second Survey, we will mail to patients an incentive packet which will include a thank you letter and a \$10 gift card for completing the survey.

Third Survey: We will issue a Third Survey packet approximately 2 1/2 months after participants complete the First Survey. This survey will take approximately 20 minutes to complete. This packet will include a letter with instructions for completing the survey in the same mode they used to complete the preceding surveys.

We will send these documents via MyHealthVet Secure Messaging if we are unable to find a current address or if patients indicate a preference to receive information through this channel. For their convenience, patients will also be given the option to use MyHealthVet Secure Messaging to send any documents that need to be returned to study staff.

Upon completion of the Third Survey, we will mail an incentive packet which will include a thank you letter and \$10 gift card.

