Analyses: The primary outcome will be weight change 12 months after brief counseling or review of health promotion literature. For this analysis, we will use a two-sample t test to evaluate the difference between the 2 arms. For any missing weight data, we will use multiple imputation. The main secondary outcomes will be changes in attempting weight loss, taking medication to prevent T2DM, or participating in a weight-related wellness program (e.g., MOVE! or DPP). For these outcomes, we will estimate mixed-effects regression models in which we will use data from the baseline, 3 month, and 12 month surveys for each participant to model individual change over time. Other secondary outcomes will be changes in mediators of engagement in behaviors to prevent T2DM such as risk perception, knowledge, motivation, and self-efficacy. For these outcomes we will also estimate mixed-effects regression models in which we will use data from the baseline, immediate follow-up, 3 month, and 12 month surveys to model individual change over time.

Interviews among participants with prediabetes will be audio-recorded and transcribed verbatim. We will conduct analyses concurrently with interviews, so early insights can inform subsequent data collection and analysis. We will code transcripts using a template analysis approach. [name] and study staff will independently review a subset of transcripts using modified grounded theory to identify salient themes. We will discuss the themes, refine them, and achieve consensus on codes and definitions. [name] and study staff will then independently code transcripts in NVivo software. First, they will independently code the same 20% subset of the transcripts. The unweighted Cohen's Kappa will then be calculated for each response and averaged to provide a single index of inter-rater reliability. Once excellent agreement is achieved, [name] and study staff will divide the remaining interview transcripts evenly and code these transcripts separately. [name] and study staff will meet regularly to discuss code summaries and memos.

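### The primary t test leaves baseline weight unused and its variance form unstated at 4:1 allocation, and a March 2019 request reopens the weight windows without defining new ones

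*Combined protocol and SAP*

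**What the plan says.** The Analyses paragraph under Data Analysis gives the endpoint, "The primary outcome will be weight change 12 months after brief counseling or review of health promotion literature", and the test, "we will use a two-sample t test to evaluate the difference between the 2 arms". It names no covariate, variance form or analysis set. On missing data it says "For any missing weight data, we will use multiple imputation". The randomization sections plan 252 participants in the Blood Test Group and 63 in the Brochure Group.

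The weights behind the endpoint are described in three places:

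- **12-month Weights:** "participants will have weight measurements at the time of their scheduled Primary Care appointment or around the time of their recall appointment date". The second weight is expected 12 months ± 1 month later.
- **Weights (under Data Analysis):** "all participants will have a weight measurement in CPRS when they undergo brief counseling or review of health promotion literature". The window is the same: "Participants who do not have a weight measurement in CPRS 12 months (± 1 month) later will be asked to come" to the clinic for one.
- **Dated updates:** The 8/10/2018 entry seeks weights from any VA facility. The 2/25/2019 entry asks for a data range of 1/27/2015 to 7/1/2018, described as running from a year before randomization to 15 months after it. An addition of 3/20/2019 asks for different baseline and follow-up observation dates, because routine weights are recorded irregularly. It gives no new windows and no rule for choosing a weight when several exist.

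**The concern.** There are two separate issues.

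**The test.** A change score fixes the coefficient of baseline weight at 1, so some precision may be lost although baseline weight is already collected. With a 4:1 split, a pooled-variance test is also sensitive to unequal SDs. If the smaller arm is more variable, the error rate rises; if the larger arm is, the test becomes conservative and loses power.

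**The outcome.** If the ± 1 month window no longer binds and nothing replaces it, two analysts could choose different baseline and 12-month weights for the same participant and reach different primary results. The request is dated after the end of the data range, so that choice could be made with the weights already in hand. A change of test does not remove this freedom; a stated weight rule does.

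**Working it through.** **Inputs from the documents.** 315 randomized at 4/5 and 1/5; 63 of the Blood Test Group projected to be in the prediabetes range; first and last randomizations 1/27/2016 and 3/31/2017; randomization about 2 weeks before the appointment; data range 1/27/2015 to 7/1/2018.

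**Assumed, because the documents give none.** Two-sided alpha of 5%, the baseline to 12-month correlation rho, SD ratios, regression slopes and the amount of missing data.

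**1. Arm sizes.** 315 × 4/5 = 252 and 315 × 1/5 = 63, as stated. No power calculation is given to reproduce.

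**2. Pooled variance at 252 vs 63.** Type I error ≈ 2 × (1 − Φ(1.96 × pooled SE / true SE)).

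- Brochure SD 1.2, Blood Test SD 1: pooled variance = (251 × 1 + 62 × 1.44)/313 = 1.087. Pooled SE² = 1.087 × (1/252 + 1/63) = 0.02157. True SE² = 1/252 + 1.44/63 = 0.02683. The SE ratio is 0.897 and the error 7.9%.
- Blood Test SD 1.2, Brochure SD 1: pooled variance = (251 × 1.44 + 62)/313 = 1.353. Pooled SE² = 0.02684, true SE² = 0.02159. The SE ratio is 1.115 and the error 2.9%.
- At a 10% difference the errors are 6.4% and 3.8%.

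In 20,000 simulated trials (rho 0.95), with the Brochure SD and then the Blood Test SD 20% larger, rejection rates were:

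| Method | Brochure SD larger | Blood Test SD larger |
|---|---|---|
| Pooled t | 7.7% | 2.9% |
| Ordinary ANCOVA | 7.7% | 2.9% |
| Welch | 4.8% | 5.0% |
| ANCOVA (common slope) with HC3 standard errors | 4.9% | 4.8% |

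So ANCOVA alone does not cure the variance problem.

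**3. Likely direction.** If only the projected 63/252 = 25% respond, by d SD, the Blood Test variance becomes 1 + 0.25 × 0.75 × d². For d = 0.5, 1 and 1.5 the SD is 1.02, 1.09 and 1.19, and a pooled SE would be 1.4%, 5.3% and 11.1% too large. That costs power; it does not inflate the error rate.

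**4. Gain from baseline adjustment.** With equal SDs at both times and a common slope, Var(ANCOVA)/Var(change) = (1 + rho)/2, and power = Φ((1.960 + 0.842)/√ratio − 1.960).

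| rho | variance ratio | power where the t test has 80% |
|---|---|---|
| 0.90 | 0.950 | 82.0% |
| 0.95 | 0.975 | 81.0% |
| 0.98 | 0.990 | 80.4% |

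Two conditions limit this gain:

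- **SD growth.** Suppose the 12-month SD is 3% larger at rho 0.95. Var(change) = 1 + 1.0609 − 2 × 0.95 × 1.03 = 0.1039. Var(ANCOVA) = 1.0609 × (1 − 0.9025) = 0.1034. The gain falls to 0.4%.
- **Unequal slopes.** Take slopes of 0.93 (Blood Test) and 1.00 (Brochure), with baseline SD 18-20 kg and residual SD 5-6 kg. A common-slope ANCOVA then has about 1.02 times the change-score variance. With an arm-by-baseline interaction the figure is 0.997-0.998.

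**5. Dates.** From 7/1/2018 to 3/20/2019 is 262 days, about 8.6 months. A ± 1 month window fits the requested range: 3/31/2017 + 14 days = 4/14/2017, and 13 months later is 5/14/2018, 48 days before 7/1/2018. The calendar range does not itself define a window for each participant. It runs from 12 months before to 29 months after randomization for the first participant, and from 26 before to 15 after for the last.

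**6. Out-of-window weights as imputation auxiliaries (illustrative only).** Let a share m lack an in-window weight, let a of those have a nearby one, and let it explain r² of the missing change. The SE ratio is √(1 − r²ma/(1 − m + ma)). For m = 0.2, r² = 0.5, a = 0.5 it is 0.972; for m = 0.4, r² = 0.8, a = 1 it is 0.825. The gain is smaller if the planned imputation would use these weights anyway.

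**The case against.** The best case for the plan is that its test is sound. A t test on change is unbiased under randomization, Welch's version is also a two-sample t test, and nothing says the pooled form was meant. The 7.9% needs the less plausible direction of unequal SDs. ANCOVA gains little, and in its common-slope form it could lose slightly at 4:1. All of this stands. What remains is that the variance form is unstated and a covariate already in hand is unused.

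Four stronger readings are tempting and are not supported:

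- **The t test is invalid.** It is not; adjustment is a matter of efficiency.
- **The documents set rival baselines.** It is true that "Trained study staff will deliver the applicable information by phone approximately 1 week after the test results are available", and that "We will mail to Brochure Group participants general health promotion information", so neither is a weighing occasion. But the blood draw is meant to fall on the day of the primary care appointment, the Brochure Group's Second Survey is issued around that appointment or recall date, and both weight descriptions rest on routine primary care weighing. The wording is loose, but it points to one visit.
- **Weights years apart will be compared.** The 2/25/2019 entry sets an extraction range. The endpoint is still change at 12 months, and no section proposes a longer interval.
- **The windows were chosen to suit the results.** The documents do not say whether weights had been compared by arm.

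The objection does not dispose of the 3/20/2019 addition. It is part of the current text, and it asks to move the observation dates without saying where to.

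**Conclusion.** The point holds in two parts of unequal weight.

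The more important part is the outcome definition. ± 1 month stands in two sections, and a later request reopens the dates for both weights without new windows or a selection rule. How far the result could move cannot be computed from the documents. The plan should settle this before arms are compared.

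The lesser part is the analysis. An unstated variance form matters only if the pooled test is used and the SDs differ: 7.9% or 2.9% at an assumed 20% difference, with loss of power the likelier direction. Baseline adjustment saves about 1-5% of variance at assumed correlations of 0.98-0.90, and less if the SD grows over the year. It is a cheap improvement, not the correction of an error.

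**What to change.** **Analysis.** State that all randomized participants are compared by arm. Use ANCOVA of 12-month weight on arm, with centred baseline weight, an arm-by-baseline interaction and heteroscedasticity-robust standard errors, combined across imputations. Report Welch's t test on change as a sensitivity analysis. If weights have already been compared by arm, keep Welch as primary and label the ANCOVA post hoc.

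**Outcome.** Reconcile 12-month Weights, Weights, the dated updates and Analyses through one dated rule, identical in both arms and fixed before weights are compared by arm:

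- Index date: the scheduled primary care or recall appointment date held at randomization.
- Baseline: the weight closest to the index date, within ± 1 month.
- 12-month weight: the weight closest to 12 months after the index date, within ± 1 month.
- Weights outside these windows: auxiliary variables in the planned multiple imputation only, never the outcome.

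Do not tie the baseline to the results call or brochure mailing. The mailing is undated and the brochure is to be read before the Second Survey is completed, so such a cut-off could remove appointment-day weights in the Brochure Group alone.

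**Cost.** Plan wording and a little analysis work, with no new patients and no data beyond the extraction requested, which still needs approval. Some participants will have no in-window weight and must be imputed, and some baseline weights may fall shortly after the information was delivered.
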